#### 9.4.7 Specific Levels of Functioning (SLOF) [33] -

The SLOF is a clinician-rated assessment that evaluates functional behaviors in the context of the individual's skills and abilities. It consists of 43 items categorized into 6 subscales: Physical functioning; Personal care skills; Interpersonal relationships; Social acceptability; Activities of community living; and Work skills. Each question is rated on a 5-point scale. The higher the total score, the better the overall functioning of the subject. According to the original version of the scale, the time frame covered by the survey is the past week. While an informant is not required for this trial, access to a person that can provide collateral (caseworker, caregiver, etc.) is preferred, as the SLOF asks them for any other relevant information, and also includes a rating for how well the informant knows the subject. The SLOF will be performed at the baseline and end of study visits.

#### 9.4.8 Physical Examination

The physical exams must be performed by the PI or designee (or a licensed medical practitioner such as a physician's assistant or nurse practitioner) listed on the site delegation of authority log.

A complete physical examination includes the following assessments: general appearance, head, eyes, ears/nose/throat, neck, lymph nodes, skin, lungs, heart, abdomen, musculoskeletal, and neurologic evaluations. If the subject is discontinued for any reason during the treatment phase, every attempt should be made to perform a final physical examination.

#### 9.4.9 Vital Signs

Arterial systolic and diastolic blood pressure and radial artery pulse rate will be measured while the patient is seated at the scheduled visits designated in the Schedule of Events in Appendix 1.

#### 9.4.9.1 Height and Body Weight

Height will be measured at the screening visit. Patients will be measured without shoes. Body weight will be recorded at screening, baseline and every visit through the 9-week treatment phase.

#### 9.4.9.2 Body Mass Index (BMI)

Body mass index (BMI) will be determined with the patient's height and weight at the screening visit and subsequent treatment visits. BMI must be calculated using the following formula: A person's (Weight in pounds divided by their height in inches squared) x 703.

#### 9.4.9.3 Waist and Hip Circumference

Waist and hip circumference will be recorded at screening, baseline, and all study visits.

#### 9.4.10 Electrocardiogram (12-Lead ECG)

The PI or a physician listed on the site delegation of authority log must review, initial, and date the report, which must be filed in the subject's study chart. Results will be captured in the subject's study chart, not in the electronic database. Clinically significant findings from the screening report must be captured in the medical history. Eligibility for study entry must be assessed by the principal investigator. Any clinically significant changes compared with baseline must be captured as AEs in the electronic database.

Individuals are to be supine for at least 5 minutes prior to ECG assessments. A central facility will be used in this study for interpretation and analysis of ECGs. All individuals will have standard resting 12-lead ECGs performed and interpreted. The time the ECG is performed will be recorded (using a 24-h clock). In addition, the time that the subject took their last dose of study medication (prior to the ECG) will be recorded on the CRF page.

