#### 9.3 Adverse Events

In a 7 week, randomized, placebo controlled trial comparing JNJ-18038683 with placebo and escitalopram (an active comparator), a total of 6 serious adverse events were reported during the study (placebo group: spontaneous abortion and suicidal ideation; escitalopram group: spontaneous abortion, suicidal ideation, suicide attempt, and chest discomfort). A total of 10 individuals (3 in the placebo group, 4 in the JNJ-18038683 group, and 3 in the escitalopram group) were withdrawn from the study prematurely due to adverse events. The 4 events leading to drop out of individuals on JNJ-18038683 were one instance each of the following: bundle branch block, panic attack, upper respiratory infection, and insomnia.

Only 3 individuals receiving the 20-mg dose of JNJ 18038683 required dose reductions at any point during the study.

Adverse events that were reported in more than 5% of individuals in any treatment group included headache, nausea, nasopharyngitis, insomnia, somnolence, dyspepsia, dizziness, dry mouth, constipation, diarrhea, vomiting, back pain, upper respiratory tract infection, palpitations, and fatigue. The treatment-emergent adverse events that were reported more frequently in the JNJ 18038683 group compared with the placebo or escitalopram groups included dyspepsia, constipation, upper respiratory tract infection, and palpitations.

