Data Analysis Plan for Northwestern- Janssen R&D Collaboration Study

Protocol Title: Testing the ability of JNJ-18038683, a selective serotonin (5-HT)7 antagonist, to

improve cognition and reduce residual depressive symptoms in stable bipolar patients

Protocol Identifier Number: 18038683BCD2001

Northwestern University IRB Number: STU00200919-MOD0042

Version: 1.13

Date: 08.04.2021

Goals:

The goals of this study are to evaluate the efficacy of JNJ-18038683 in an 8-week trial to ameliorate the cognitive deficit and reduce residual depressive symptoms in 60 stable bipolar outpatients receiving treatment for depression. JNJ-18038683 will be studied and compared with placebo as adjunctive treatment to standard pharmacologic treatment for bipolar disorder. Sixty patients will be enrolled and randomized with a 1:1 ratio to one dose of JNJ-18038683 or placebo providing 30 subjects for each treatment arm. The initial intention was to follow stratified randomization based on the presence/absence of atypical APDs with 5-HT7 antagonism so that there is a balance in the assignment of active treatment and placebo in individuals who are and are not, receiving atypical APDs with 5-HT7 antagonism. However, due to recruitment difficulties, the stratified randomization method was not able to be followed as anticipated and was amended.

Assessments and Events:

Demographics, medical history, physical examination, serum pregnancy test, urine drug test, SCID-I diagnosis, and screening neurocognitive assessments will be done only during the screening visit. Urine pregnancy testing is performed at the baseline visit.

Table 1: Assessments completed during the screening visit only

Event /Assessment	Screen
Medical History & Demographics	X
Physical Examination	X
Serum Pregnancy Test	X
Urine Drug Screen	X
Inclusion/Exclusion Criteria	X
SCID-I	X
Screening neurocognitive assessments	X

Neurocognitive battery will be the primary measure of interest and evaluated at baseline and 8 weeks. The clinical global severity scores (CGI-BP), Young Mania Rating (YMRS), Scale for Tardive Dyskinesia (AIMS), Montgomery Asberg Depression Rating Scale (MADRS), Electrocardiogram and Clinical Safety Laboratory Tests will be collected at screening or baseline, and at 4 and 8 weeks. A measure of functional ability (SLOF) also will be assessed at baseline and 8 weeks. The schedule of these assessments is listed in table 2.

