Secondary analyses related to efficacy:

The secondary analyses regarding change in verbal fluency test scores will include identification of patients in each arm who improved in verbal fluency scores. The analysis plan includes exploring the effect of concomitant meds, gender or race that might contribute to treatment response. For this purpose, improvement in verbal fluency can be grouped as a dichotomous response and used as a dependent variable in a logistic regression model. The usual method of grouping will be improvement of ≥0.5 SD from the baseline scores. Using this model, the odds of improvement in verbal fluency can be compared in the active treatment group against the placebo group. In this model, the variables, age, gender, lab values and presence/absence of concomitant meds, baseline MADRS total score, YMRS and Clinical Global Severity score mania or depression severity may influence performance on cognitive testing and will be tested as potential covariates using one or few covariates at a time due to sample size restrictions.

Additional secondary analyses will study the effect of treatment group on other cognitive and behavioral measures including: 1) Digital Symbol Task, 2) Brown-Peterson Consonant Trigram Memory Task, 3) WISC-III Mazes; 4) Wisconsin Card Sorting Test; 5) MADRS total score,6) YMRS, and 7) Clinical Global Severity score using a mixed model repeated measure ANCOVA as described above. If indicated, variables such as age, gender, concomitant meds, will be examined, as will be done for the primary outcome measure.

Adverse Events:

A tabular summary of all anticipated and unanticipated serious or non-serious adverse events will be presented, including drop-outs due to any side effects or safety reasons. For each serious or other adverse events, the summary includes the adverse event term, affected organ system, number of participants at risk, and number of participants affected, by the study arm or comparison group. Using appropriate parametric or non-parametric methods, each type of adverse event will be compared between groups. All adverse events, e.g. development of suicidal ideation or behaviors or switch to mania/hypomania, will be examined thoroughly for impact on primary and secondary outcome measures. We will assess group differences, excluding subjects without these two side effects.

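### ECG results reach the analysis database only as adverse events, so interval shifts below the clinical-significance threshold would not be seen by arm

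*Protocol*

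**What the plan says.** Protocol section 9.4.10 gives the storage rule: ECG results go in the "study chart, not in the electronic database". It makes one exception for ECGs after screening: "Any clinically significant changes compared with baseline must be captured as AEs in the electronic database". Significant screening findings go into the medical history.

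The same section provides for central reading: "A central facility will be used in this study for interpretation and analysis of ECGs". It also asks for the clock time of each ECG, and the time of the last dose before it "will be recorded on the CRF page".

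The schedules in protocol section 7.0 and Appendix 1 place ECGs at screening, Day 28 and Day 56. The SAP agrees: "Electrocardiogram and Clinical Safety Laboratory Tests will be collected at screening or baseline, and at 4 and 8 weeks", and its Table 2 shows the same three time points. The SAP then gives no ECG analysis. Its only relevant comparison is in the adverse event section, where "each type of adverse event will be compared between groups".

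On prior experience, protocol section 9.3 lists the four events that led to dropout on JNJ-18038683 in the earlier trial: "bundle branch block, panic attack, upper respiratory infection, and insomnia". It also names palpitations among the events seen more often on the drug than on placebo or escitalopram.

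**The concern.** The trial goes to the trouble of taking up to three ECGs per participant, having them read centrally and recording dose timing for each one. The storage rule then keeps the measurements out of the data that the statistician will receive. What gets through is a yes/no judgement of clinical significance, for which section 9.4.10 sets no threshold.

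A drug effect on heart rate or conduction can appear as a modest average shift that is unremarkable in any one participant. Such a shift would generate no adverse event and so would leave no trace in the planned data. Section 9.3.2 names ECGs among the tests by which all participants should be closely monitored, and the earlier trial had one conduction-related withdrawal on this drug. A by-arm description of the ECGs already being collected is therefore a reasonable thing to expect. What is at stake is safety information, not any efficacy result.

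**Working it through.** No figure in the documents lies behind this point, so there is none to reproduce. The check is first a reading of the data path, then an illustration of what each route could show.

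**Data path**

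1. Section 11.2: study data are entered in REDCap, and analysis files are extracted from it.
2. Section 9.4.10: ECG results are not entered in the electronic database; changes judged clinically significant are entered as adverse events.
3. From 1 and 2: the analysis files hold ECG-related adverse events, but no heart rate, PR, QRS or QTc value and no normal/abnormal category.
4. Section 9.4.10 assigns interpretation and analysis to a central facility, but describes no transfer of its results to the database.
5. Section 8.0 lists weight, BMI, waist circumference and movement scales as tolerability measures. ECG is not among them, and the SAP adds no ECG table.

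**Volume.** 60 participants (section 22.0) × 3 scheduled ECGs = 180 at most. Of these, 60 are screening tracings and 60 × 2 = 120 are on treatment.

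**What the adverse event route can show.** Section 22.0 gives 30 per arm. Under Fisher's exact test (two-sided 0.05) with no events on placebo:

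- 0 of 30 v 5 of 30: p = 2 × C(30,5)/C(60,5) = 2 × 142,506/5,461,512 = 0.052
- 0 of 30 v 6 of 30: p = 2 × C(30,6)/C(60,6) = 2 × 593,775/50,063,860 = 0.024

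So six flagged participants on the drug against none on placebo are needed. The documents give no event rates; the following are assumptions:

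- 0% v 5%: power 0.3%
- 0% v 10%: power 7%
- 3% v 13%: power 9%
- 3% v 20%: power 34%

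**What captured intervals could show.** Let d be the arm difference in a continuous ECG measure, in units of that measure's SD. Normal approximation, n = 30 per arm, two-sided 0.05:

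- Half-width of the 95% interval = 1.96 × √(2/30) = 0.51 SD
- Power = Φ(d × √(30/2) − 1.96). For d = 0.5: 0.5 × 3.873 − 1.96 = −0.024, so power is 49%. The same formula gives 21% for d = 0.3, 77% for d = 0.7 and 83% for d = 0.75.

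The two sets of scenarios are not matched, so they do not measure how much one route gains over the other. They show that flagged events alone say little at this size, and that interval data would give an estimate with a usable but wide interval.

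**The case against.** A reader might infer that the trial cannot compare ECG changes by arm at all. The documents do not support that. Clinically significant changes must be entered as adverse events, and the SAP compares each adverse event type between groups. Palpitations are themselves an adverse event and are fully covered by that route.

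Nor do the documents support these further inferences:

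- That the measurements are lost or kept only on paper. Section 9.4.10 says study chart, without giving its form, and the tracings are also read centrally. The values could be retrieved; the plan simply does not provide for it.
- That a site investigator alone decides what is significant. A site physician reviews and signs each report, but who judges on-treatment significance is not stated.
- That there is a known repolarisation problem. Nothing in the documents describes one.

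The prior signal is also thin. It consists of one bundle branch block, with no denominator or attribution, and palpitations without rates. Section 9.3 lists no serious adverse event in the JNJ-18038683 group, and section 2.1.2 says that the earlier trial raised no safety concern.

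Finally, the SAP gives no by-arm analysis for vital signs or safety laboratory tests either. Its safety plan rests on adverse events throughout, so the ECG storage rule is not the only cause of the gap. And at 30 per arm, small shifts would probably be missed even with the intervals in hand.

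All of this stands, and it limits the point. It does not remove it: the storage rule is explicit, the ECGs are scheduled and centrally read in any case, and the adverse event route cannot register a shift that stays below each participant's threshold.

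**Conclusion.** The point holds in a limited form. Under the plan as written, ECG information enters the analysis data only as adverse events judged clinically significant. Intervals and abnormality categories are absent, and no by-arm ECG summary is specified. Flagged changes can be compared between arms; sub-threshold shifts cannot be seen without an unplanned retrieval from the charts or the central facility.

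The size is modest: at most 180 ECGs, 120 of them on treatment, and a descriptive comparison with a half-width of about 0.5 SD. That figure assumes all 30 per arm contribute; dropouts would widen it. The power figures rest on assumed rates and effect sizes. No efficacy conclusion, error rate or eligibility decision depends on this. It is worth correcting because the data will exist anyway, and a summary specified before unblinding is more credible than one assembled afterwards.

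**What to change.** - **Protocol section 9.4.10.** Replace the chart-only rule. State that the centrally read heart rate, PR, QRS, QTc and overall interpretation at each scheduled ECG are entered in, or transferred to, the study database. Reconcile the central analysis with the present storage rule, and state who judges clinical significance on treatment. Name the screening ECG as the baseline, since it is the only one scheduled before treatment.
- **SAP.** Add one descriptive table by arm: change from screening to Day 28 and to Day 56 for each measure, with 95% intervals for the arm difference, and counts of new abnormalities. Say that it is descriptive and cannot rule out small shifts. Specify it before the blind is broken.

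The cost is data entry or transfer for at most 180 ECGs, one CRF page and one table. No visit, procedure or clinical rule changes.

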#### 9.4.11 Adverse Event (AE) Monitoring

The PI or a designee (eg, a licensed, qualified medical practitioner such as a physician's assistant or a nurse practitioner) listed on the site delegation of authority log must assess the severity and relationship to study medication(s) of all AEs. All observed or volunteered AEs regardless of treatment group or

suspected causal relationship to the investigational product(s) will be recorded on the AE page(s) of the electronic database.

For all AEs, the investigator must pursue and obtain information adequate both to determine the outcome of the AE and to assess whether it meets the criteria for classification as an SAE requiring immediate notification to the Sponsor or its designated representative.

For all AEs, sufficient information should be obtained by the investigator to determine the causality of the AE. The investigator is required to assess causality and indicate that assessment on the source document and electronic database. For AEs with a causal relationship to the investigational product, follow-up by the investigator is required until the event or its sequelae resolve or stabilize at a level acceptable to the investigator.

Adverse events (serious and non-serious) should be recorded on the source document and electronic medical record from the date the informed consent form (ICF) was signed until the end of their participation in the study, ie, the subject has discontinued or completed the study.

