#### 9.0 Procedures Involved

Study visits will include screening and 6 visits (baseline, Weeks 1, 2, 4, 6, and 8). Please see Appendix 1 – Schedule of Assessments

At screening, the Structured Clinical Interview for Diagnosis for DSM Disorders (SCID) will be completed for confirmation of psychiatric diagnosis. A medical/psychiatric history will also be collected and a physical exam will be performed. Vital signs including weight, height, waist and hip measurement will be obtained at screening to record body mass index. The Hopkins Verbal Learning Test (HVLT) and Trail Making Test A (TMT-A), will be administered to screen for severity of cognitive impairment. Only individuals who score between the 25th and 75th percentile as compared to normative data on these tasks will be enrolled.

If the subject is determined eligible during the screening procedure, which can last for up to two weeks, a baseline visit will be scheduled. Baseline assessments of cognitive function, psychopathology and global function will be administered along with movement ratings at the baseline visit. Functional outcome will be assessed with Specific Level of Function Scale (SLOF) [33]. Adverse events will be collected and recorded from the time the subject signs the informed consent to the final safety follow-up visit, and motor side effects will be monitored by the Abnormal Involuntary Movement Scale at the following visits: baseline, Weeks 4 and 8.

Individuals will be randomized to receive JNJ-18038683 or placebo after the completion of the baseline assessments. Individuals will be stratified for randomization as either being treated with an AD or not being treated with an AD. As in the previous study of JNJ-18038683 for depression, individuals randomized to JNJ-18038683 will receive 10 mg for one week, then titrate to 20 mg, with the provision for a single, downward dose adjustment for intolerance, based upon investigator judgment. No antipsychotic drugs which are 5-HT7 antagonists will be permitted to avoid effects upon 5-HT7 receptors from enhanced 5-HT concentrations and possible down regulation of 5-HT7 receptors. As JNJ-18038683 is a competitive inhibitor of CYP2D6, there will be a 2 week washout period requested after the trial prior to initiation of any CYP2D6 substrates (see Appendix 2).

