Individuals will be asked to return to the clinic at study weeks 1, 2, 4, and 6 after baseline to monitor for side effects and compliance. At the Week 4 visit, efficacy assessments will be completed (MADRS, YMRS and CGI-BP). Between clinic visits, research staff will complete phone calls with individuals at study Weeks 3, 5, and 7. Individuals will return for a final study visit 8 weeks after initiation of the randomized study medication. A Safety Follow-up phone call will take place 4 weeks after the final visit and safety assessments will be completed (C-SSRS, Adverse Events, Concomitant Medications). The assessments completed at baseline will be repeated at this Week 8 visit (See Appendix 1 – Schedule of Assessments). Reasons for early termination will be recorded. Every effort will be made to obtain appropriate rating scale data at the final visit of early terminators.

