### 9.3.7 Reporting Requirements for Adverse Events

#### **Expedited Reporting**

- The Principal Investigator must be notified within 24 hours of learning of any serious adverse events, regardless of attribution, occurring during the study or within 30 days of the last administration of the study drug.
- The investigator or site personnel will inform Janssen within 24 hours of notification of any serious adverse event by phone or fax, with follow-up with a written narrative of the event within 48 hours.
- The Northwestern University Institutional Review Board must be notified within 10 business days of "any unanticipated problems involving risk to individuals or others"

The following events meet the definition of Unanticipated Problem Reporting (UPR):

- 1. Any serious event (injuries, side effects, deaths or other problems), which in the opinion of the Principal Investigator was unanticipated, involved risk to individuals or others, and was possibly related to the research procedures.
- 2. Any serious accidental or unintentional change to the IRB-approved protocol that alters the level of risk.
- 3. Any deviation from the protocol taken without prior IRB review to eliminate apparent immediate hazard to a research subject.
- 4. Any new information (e.g., publication, safety monitoring report, updated sponsor safety report), interim result or other finding that indicates an unexpected change to the risk/benefit ratio for the research.
- 5. Any breach in confidentiality that may involve risk to the subject or others.
- 6. Any complaint of a subject that indicates an unanticipated risk or that cannot be resolved by the Principal Investigator.
- The FDA will be notified within 7 business days of any unexpected fatal or life-threatening adverse event with possible relationship to study drug, and 15 business days of any event that is considered: 1) serious, 2) unexpected, and 3) at least possibly related to study participation.

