#### 9.3.8 Unblinding Procedures

The blind should not be broken unless subject has completed all study procedures and the data has been locked. Emergency unblinding is expected to be infrequent.

Emergency unblinding should occur only if the principal investigator (or other treating physician) considers breaking the blind medically relevant. All individuals who have the blind broken will be discontinued from the study. Documentation of the reasons for unblinding, including date and time will be recorded in the source documents and the electronic case report form (eCRF).

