#### 13.0 Withdrawal of Individuals\*

Individuals can be taken off the study treatment and/or study at any time at their own request, or they may be withdrawn at the discretion of the investigator for safety, behavioral or administrative reasons. The reason(s) for discontinuation will be documented and may include:

- Individual voluntarily withdraws from treatment (follow-up permitted);
- Individual withdraws consent (termination of treatment and follow-up);
- Individual is unable to comply with protocol requirements;
- Individual experiences toxicity that makes continuation in the protocol unsafe:
- Physician judges continuation on the study would not be in the patient's best interest;
- Individual becomes pregnant (pregnancy to be reported along same timelines as a serious adverse event).

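### For patients discontinued early, Protocol 9.4.11 stops adverse event recording at discontinuation while 9.0 runs it to the safety call, and the SAP does not separate pre-dose, on-treatment and post-treatment events

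*Protocol*

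**What the plan says.** **When recording ends.** Protocol 9.4.11 starts AE recording at consent and continues it "until the end of their participation in the study, ie, the subject has discontinued or completed the study". Section 9.0 has the same start and a different end: "Adverse events will be collected and recorded from the time the subject signs the informed consent to the final safety follow-up visit". It places that follow-up after the last clinic visit: a "phone call will take place 4 weeks after the final visit and safety assessments will be completed (C-SSRS, Adverse Events, Concomitant Medications"). The same section expects early terminators to have a final visit too. Both protocol schedules and the note to SAP Table 3 mark AE assessment at Day 84.

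**Who is discontinued early.** Section 9.3.8 says "All individuals who have the blind broken will be discontinued from the study". Section 13.0 lists six withdrawal reasons. One permits follow-up (withdrawal from treatment only), one ends it (withdrawal of consent), and four do not say. Among those four is "Individual experiences toxicity that makes continuation in the protocol unsafe".

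**What else covers AEs.** Section 9.3.7 requires notification of serious AEs "occurring during the study or within 30 days of the last administration of the study drug". Section 9.3.4 monitors every AE, related or not, until it resolves, returns to baseline, is otherwise explained, or the patient dies. Section 9.3.5.1 defines an AE as occurring in a patient on study treatment.

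**What the SAP does with AEs.** The Assessments and Events section lists AE collection from screening to Day 84. The Adverse Events section tabulates all AEs, says "each type of adverse event will be compared between groups", and adds that all AEs, with suicidality and mood switch as examples, "will be examined thoroughly for impact on primary and secondary outcome measures". It then plans a group comparison that leaves out subjects who had neither of those two.

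**The concern.** A site that follows 9.4.11 as written would stop recording new AEs on the day a patient is discontinued from the study. A site that follows 9.0 would ask again four weeks later. Patients stopped for toxicity or after emergency unblinding are among those affected, and the weeks after they stop are a period in which one would want complete safety data. If more patients discontinue in one arm than the other, the recording time would also differ between arms.

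On the SAP side, a collection schedule says when staff ask about AEs. It does not say which recorded events enter the comparison. Taken literally, all AEs include events from screening, before any study drug, and events after the last dose. Pooling these with on-treatment events tends to pull a risk ratio toward 1, the unwelcome direction in a safety comparison. The AE-impact analysis has a related problem: a first event after Day 56 could place a patient in the subset although it cannot have affected a score taken at Day 56.

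**Working it through.** The plan states no figure to reproduce. The check sets the rules side by side, then does day-count arithmetic and an illustration.

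**1. The two rules by type of patient**

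| Patient | 9.4.11 ends recording | 9.0 ends recording | Difference |
|---|---|---|---|
| Completer, final visit Day 56 | Study completed, which can include the Day 84 call | Day 84 | 0 days on that reading |
| Discontinued, final visit Day 14 (illustrative) | Day 14 | Day 14 + 28 = Day 42 | 28 days |

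**2. What is left uncovered.** Section 9.3.7 covers serious AEs in both rows. Section 9.3.4 covers AEs that had already begun. What remains is a new, non-serious AE starting after discontinuation.

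**3. Size of the recording loss.** Let k of 60 patients discontinue, on average at Day 28 (assumed). Patient-days from first dose under 9.0 are (60 − k) × 84 + k × (28 + 28). Those lost under 9.4.11 are k × 28.

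- Section 11.1 recruits 36 per group for 33 needed: (36 − 33)/36 = 8.3%, and 8.3% of 60 is 5. Total 55 × 84 + 5 × 56 = 4,900; lost 140, or 2.9%.
- Assumed 20%, k = 12: lost 336 of 4,704, or 7.1%.
- Assumed 30%, k = 18: lost 504 of 4,536, or 11.1%.

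The loss is charged to every dropout, including those who withdraw consent and could not be followed anyway, so at each rate it is an upper figure.

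**4. Span of collected events.** For a completer: up to 14 days of screening (9.0), 56 days of treatment and 28 days to the call, 98 in all. Days off drug are 14 + 28 = 42, and 42/98 = 43%. This takes dosing to run to Day 56.

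**5. Illustration for one AE type, under assumed rates.** Assume a constant background rate λ = −ln(1 − p₀)/56, where p₀ is the placebo risk over Days 1–56. Assume the drug doubles the rate while it is taken and has no effect afterwards. Over a window of T days, placebo risk is 1 − exp(−λT) and drug risk is 1 − exp(−λ(T + 56)). With p₀ = 10% and 30 per arm:

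| Events counted | T | Placebo risk | Drug risk | Patients affected | Risk ratio | Difference (points) |
|---|---|---|---|---|---|---|
| Day 1–56 | 56 | 0.100 | 0.190 | 3.0 v 5.7 | 1.90 | 9.0 |
| Day 1–84 | 84 | 0.146 | 0.232 | 4.4 v 6.9 | 1.58 | 8.5 |
| Consent–Day 84 | 98 | 0.168 | 0.252 | 5.1 v 7.5 | 1.49 | 8.3 |

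With p₀ = 5% the ratio goes from 1.95 to 1.53. With p₀ = 20% it goes from 1.80 to 1.42.

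**The case against.** **The protocol gap is narrow.** The end of participation in 9.4.11 could be taken to include the safety call, and 9.0 ties that call to a final visit that early terminators also have. Section 9.3.6 refers to all events within 30 days of the last dose, not only serious ones. The toxicity that led to a discontinuation is itself recorded and followed under 9.3.4. Much of this stands. But 9.4.11 goes on to define the end of participation as having discontinued or completed, and the 9.3.6 text belongs to the steps for expedited reporting. Neither clearly restores routine recording of a new non-serious AE in a discontinued patient.

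**The SAP is not silent.** A reader might infer that it gives no start or end for AEs at all. It does not support that: it gives a collection schedule from screening to Day 84, and the definition in 9.3.5.1 points away from pre-dose events. The consent-to-Day-84 row above is therefore the broadest reading, not the established plan. What stands is that protocol recording begins at consent, the SAP says all AEs, and nothing sorts them by treatment period.

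**The numbers are soft.** The AE rates, the doubling, the constant hazard and the Day 28 average are all assumed. Section 9.0 requests a two-week washout before CYP2D6 substrates, so the days just after the last dose may not be free of drug effect. The 8.3% allowance belongs to the 36-per-group calculation, while section 22.0 and the SAP give 30 per arm. The risk difference hardly moves at p₀ = 10%. With 30 per arm, a two-sided Fisher exact test at 5% would have power of only 7.8%, 7.2% and 6.9% over the three windows, so no choice of window yields a useful test for a single AE type. All of this stands, and it limits the claim to clear description of the safety data.

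**Other safety data exist.** Protocol 8.0 promises tolerability analyses of weight, BMI, waist and movement scales, and the SAP compares YMRS and MADRS by arm. That is correct, but it does not fill a gap in AE recording.

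**Conclusion.** The point holds in a limited form. For patients discontinued before Week 8, 9.4.11 and 9.0 give different ends to AE recording, 28 days apart when the call follows that patient's final visit. The events at risk are new, non-serious AEs. The loss is 2.9% of patient-days at the dropout allowance in 11.1, and 7.1% to 11.1% at an assumed 20% to 30%. The SAP compares AEs by arm and relates them to Day 56 outcomes without separating pre-dose, on-treatment and post-treatment events.

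Several stronger readings are tempting and not supported. Completers face no conflict, because their recording can be read to Day 84 in both sections. Patients stopped for toxicity do not lose all safety follow-up, because 9.3.4 and 9.3.7 still apply to them. The change in risk ratio from 1.90 to 1.49 is not an estimate for this trial: the documents give no AE rate for this population and no dropout rate by arm, so the size and direction of any bias from unequal discontinuation cannot be computed. The primary efficacy analysis is not affected.

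**What to change.** 1. **Protocol 9.4.11:** end AE recording at the safety call 4 weeks after the final visit (Day 84 for completers). Apply this to everyone who took study drug and has not withdrawn consent, naming patients discontinued under 9.3.8 and section 13.0.
2. **SAP, Adverse Events:** compare arms on AEs that start or worsen after the first dose, among all patients who took at least one dose. Show on-treatment and post-last-dose events separately by arm. List pre-dose events without comparison.
3. **SAP, AE-impact analysis:** count only AEs with onset after the first dose and on or before that patient's Week 8 assessment.

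These are text edits, best made before unblinding. No new type of contact is needed, since the safety call already exists. For early terminators it means at most about 5 calls at the 8.3% allowance, or 12 to 18 at 20% to 30% dropout. AE onset dates, and last-dose dates for the split in item 2, have to be in the database.
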